Following study recruitment, subjects will be asked to take EyeSimplify visual field tests at home biweekly for six months. They will have no additional responsibilities between tests. Subjects will access the EyeSimplify web browser on their personal electronic devices using a link and login credentials provided to them by a research assistant. Upon logging into the EyeSimplify web browser, subjects will click the "Start Test" button found along the left side of the window and follow the prompts presented on screen to calibrate their screen. Screen calibration involves holding a driver's license/credit card/ID to the screen to ensure the test window is the appropriate dimensions. Following screen calibration, subjects will follow the test prompts presented on screen to complete their visual field test. Test results are automatically sent to the research assistant who issued the exam, so subjects may exit the browser after each test. Upon study completion, subjects will be asked to fill out a brief satisfaction survey.

M&S Technologies is the developer of the EyeSimplify web-based visual field test. [name], [name], and [name] have no financial or intellectual relationship with M&S Technologies, aside from the current study and an additional study under IRB review investigating the Pico Virtual Reality Headset visual field test.

As the developers of the web-based visual field test, M&S Technologies maintains a secure, encrypted, HIPAA-compliant database of EyeSimplify users. This database includes patient profiles containing unique patient IDs (de-identified), birth year, and visual field testing results. Outside of this testing information, M&S Technologies does not have access to any additional patient information.

I.5

Specify your research question(s), study aims or hypotheses (do not indicate "see protocol")
Aim 1: Determine test reliability of the EyeSimplify (M&S Technologies, Niles, IL) home, web-based visual field test in glaucoma patients.
Aim 2: Determine the concordance of EyeSimplify to the Humphrey Visual Field Analyzer (Carl Zeiss Meditec Inc., Dublin, CA) in identifying visual field loss progression.
Aim 3: Determine patient compliance with and tolerance of biweekly EyeSimplify testing for a 6 month period, assessed by test recordkeeping and a patient experience survey.

Primary Hypothesis: The EyeSimplify visual field test will produce reliable visual field testing data.

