Secondary Hypothesis: The EyeSimplify visual field test will be non-inferior to the Humphrey Visual Field Analyzer in identifying glaucomatous progression trends.

I.6

Background and significance and/or Preliminary studies related to this project. (do not indicate "see protocol")
Glaucoma is the leading cause of irreversible blindness worldwide (1-2). Standard Automated Perimetry is the current accepted standard for diagnosis and monitoring of glaucomatous visual field loss (3), and the Humphrey Visual Field Analyzer (HFA; Carl Zeiss Meditec Inc., Dublin, CA) is the automated perimeter that is most frequently used due to it currently having the largest market share. The HFA is a useful clinical tool; however, it is a large, expensive device. Testing takes approximately seven minutes per eye when using the Swedish Interactive Threshold Algorithm (SITA) Standard testing algorithm, and testing is typically only done at 6-12 month intervals. Recently, there has been interest in the development of alternative methods to monitor visual field progression outside of the clinic setting (4). EyeSimplify (M&S Technologies, Niles, IL) is a web-based visual field test that aims to increase the frequency at which patients can test their visual fields, improve accessibility to visual field testing, and potentially identify visual field loss progression more quickly.

I.7

Literature cited / references (if attaching a grant or protocol enter N/A).
1. Quigley HA. Number of people with glaucoma worldwide. Br J Ophthalmol. May 1996;80(5):389-93. doi:10.1136/bjo.80.5.389

doi:10.1136/bjo.2005.081224

II. Research Team

II.1

Principal Investigator

Name	E-mail	College
[name]	[contact]	Carver College of Medicine

II.2

Team Members

UI Team Members

Name	E-mail	College	Contact	Key Prsn	UI COI	VAMC COI	Consent Process Involvement	Deactivated
[name]	[contact]	Carver College of Medicine	Yes	Yes	No		Yes	No

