- Describe study populations separately if they will be participating in different procedures - include CONTROL population if applicable.*
- DESCRIBE:**
- *What subjects will be asked to do/what happens in the study (in sequential order)*
 - *The time period over which procedures will occur*
 - *The time commitment for the subject for individual visits/procedures*
 - *Long-term followup and how it occurs*
- Potential subjects will be approached at the time of their regularly scheduled appointment to participate in this research study. The research assistant will answer any questions potential subjects may have regarding the purpose, procedure, and risks of the study. If they agree to participate, subjects will sign an informed consent.
- In addition to routinely scheduled clinical examination, including visual field testing (VF) with the Humphrey Field Analyzer (HFA), subjects will be asked to complete biweekly VF for six months using EyeSimplify, a novel, web-based VF, at home. Subjects will be instructed to complete the EyeSimplify VF in a quiet, dark room free of distractions. The research assistant will be available via email or telephone to troubleshoot any issues that may arise.
- The EyeSimplify uses a 24-2 examination protocol with a Neighborhood-Zippy Estimation by Sequential Testing (ZEST) testing algorithm. Background brightness will be set to 15.8 ASB. The test will use a scaled white stimulus. Subjects will self-administer the EyeSimplify VF at home. The EyeSimplify VF will be deemed unreliable if FP >15%. The HFA uses a 24-2 examination protocol with a SITA standard testing algorithm. A clinical technician will administer the HFA VF at the University of Iowa Hospitals and Clinics' Glaucoma clinic. The HFA VF will be deemed unreliable if FP >15%. At the conclusion of the study, subjects will complete a satisfaction survey regarding testing using the EyeSimplify VF.
- VII.E.7** *Will you attempt to recontact subjects who are lost to follow-up?*
Yes
- VII.E.8** *Describe - any procedures need to be included in the consent:*

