- Electronic records (computer files, electronic databases, etc.) - All electronic files will be kept as files on an encrypted, password-protected UIHC Department of Ophthalmology network server. There will be no identifiers or link available on any transferred data; therefore, there will be no way to compromise patients' privacy or confidentiality.
 - Name - [name]
 - Title - Senior IT Support Consultant
 - University Job Classification - Faculty/Staff
- Paper/hard copy records (hard copy surveys, questionnaires, case report forms, pictures, etc.) - Informed consent documents will be transported directly from the UIHC Glaucoma clinic to a locked file cabinet in the PI's office within the Department of Ophthalmology and Visual Sciences immediately following the study recruitment clinical encounter by the PI or research assistant. These documents will remain in this locked cabinet for the duration of the study.

X.5 Do the confidentiality protections indicated above allow only members of the research team to access the data/specimens?

No

X.6 Describe

M&S Technologies, the developers of the EyeSimplify web-based visual field test, maintain a secure, encrypted, HIPAA-compliant database of patient testing information. This database includes study ID (de-identified), birth year, and experimental visual field testing data. M&S Technologies does not have access to any additional patient information.

X.7 Does your study meet the NIH criteria for a [Certificate of Confidentiality](#) or will you be applying for Certificate of Confidentiality?

No

XI. Data Analysis

XI.1 Describe the analysis methods you will use, including, if applicable, the variables you will analyze

Variables: Clinical data including age, gender, ethnicity, Humphry Visual Field performance, EyeSimplify Visual Field performance, and satisfaction survey will be collected and analyzed.

Data analysis: Humphrey Visual Field Guided Progression Analysis (GPA) and EyeSimplify Visual Field mean deviation linear trending will be compared using Bland-Altman analysis.

XI.2 Provide the rationale or power analysis to support the number of subjects proposed to complete this study.

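### The secondary hypothesis claims non-inferior progression detection, but the plan has no margin, decision rule or progression criterion, and its only analysis is Bland-Altman agreement

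*Combined protocol and SAP*

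**What the plan says.** The secondary hypothesis in I.5 is that "The EyeSimplify visual field test will be non-inferior to the Humphrey Visual Field Analyzer in identifying glaucomatous progression trends". The matching aim asks for less: "Aim 2: Determine the concordance of EyeSimplify to the Humphrey Visual Field Analyzer" in identifying progression of field loss.

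XI.1 names one analysis. It opens with "Data analysis: Humphrey Visual Field Guided Progression Analysis (GPA" as the HFA side and sets this against the home test: "EyeSimplify Visual Field mean deviation linear trending will be compared using Bland-Altman analysis". The documents give no margin, significance level, confidence-bound rule, definition of progression or acceptable limits of agreement. XI.1 does not say which output of the HFA progression analysis is used, or over what period.

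On timing, VII.E.6 says "subjects will be asked to complete biweekly VF for six months using EyeSimplify". HFA belongs to routine care: "In addition to routinely scheduled clinical examination, including visual field testing (VF) with the Humphrey Field Analyzer (HFA". No HFA field is timed by the study. The background in I.6 says of usual HFA practice that "testing is typically only done at 6-12 month intervals". I.4 adds that records are also collected retrospectively and lists HFA performance among the recorded data, without saying how many earlier fields are used.

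XI.2 answers the power question with a precedent only: a similar study that recruited 47 subjects and analysed 20.

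**The concern.** Non-inferiority is a decision. It needs a performance measure, a largest acceptable loss on that measure, and a rule that compares a confidence bound with that loss. Bland-Altman limits describe how far two measurements differ. Without a limit fixed in advance they neither accept nor reject anything.

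Without such a rule, two imprecise methods that both show little change over six months could be reported as concordant or non-inferior. This is one of only two stated hypotheses, and it takes up the only analysis sentence in XI.1. VII.B.32 reports no prior research on this test, so an unsupported claim would have no other evidence to check it against.

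**Working it through.** **1. The plan's own figure.** 20/47 = 42.6%, which rounds to the stated 43%. The target of 50 cannot be reproduced, because no significance level, power, SD, effect size or margin is given. If the same share were analysed here, 50 × 20/47 = 21 subjects. That is an assumption: the precedent used a different device and ran for twelve months.

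**2. Claim against analysis.**

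| Needed for non-inferiority | In the documents |
|---|---|
| Measure of progression detection | Not defined |
| Both devices on one scale | HFA output not specified; EyeSimplify is an MD slope |
| Margin | None |
| Confidence-bound rule | None |
| Reference fields at set times | HFA at routine visits only |

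This step needs no assumption and decides the point.

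**3. HFA fields in the window.** If the 6 to 12 month interval applies, six months hold about 1 to 2 fields. One field gives no slope. For two fields at 0 and 0.5 years, Sxx = 2 × 0.25² = 0.125, so the slope SE is SD/√0.125 = 2.83 × SD dB/year, with no residual degrees of freedom. If earlier fields are used, say five at half-year spacing over two years, Sxx = 2.5 and the SE is 0.63 × SD. That is more precise, but it covers a different period from the home tests.

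**4. EyeSimplify slope for one subject.** SE = SD/√Sxx. Assumptions: SD 1.0 to 1.5 dB, equal spacing, no missed tests. *Biweekly* is not defined, so both readings are shown.
- Every two weeks, 13 tests: Sxx = 182 × (1/26)² = 0.2692, so SE = 1.93 to 2.89 dB/year.
- Twice a week, 52 tests: Sxx = 11,713 × (1/104)² = 1.083, so SE = 0.96 to 1.44 dB/year.

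The chance of flagging a true loss at one-sided 5% is 1 − Φ(1.645 − rate/SE).

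| True loss | 13 tests | 52 tests |
|---|---|---|
| 1 dB/year | 10–13% | 17–27% |
| 2 dB/year | 17–27% | 40–67% |

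**5. What a margin on mean slope would have to be.** Take 13 home tests, HFA fields at 0 and 6 months, the same SD on both devices, and no true difference or between-subject variation in it. The SD of the paired slope difference is then √(1/0.2692 + 1/0.125) × SD = √(3.714 + 8) × SD = 3.42 × SD. The smallest margin with 80% power at one-sided 2.5% is (1.96 + 0.84) × 3.42 × SD/√n.

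| SD (dB) | n = 50 | n = 21 |
|---|---|---|
| 0.5 | 0.7 dB/year | 1.0 dB/year |
| 1.0 | 1.4 dB/year | 2.1 dB/year |
| 1.5 | 2.0 dB/year | 3.1 dB/year |

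**6. Precision of agreement limits.** With one pair per subject, the 95% CI half-width of each limit is t × SDd × √(1/n + 1.96²/(2(n − 1))), where SDd is the SD of the paired differences. This gives 0.49 × SDd at n = 50 and 0.79 × SDd at n = 21.

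**The case against.** The claim is secondary, Aim 2 already asks for concordance, and Bland-Altman suits concordance. This stands, and it shows that the remedy is mainly one of wording. It does not give the hypothesis a test.

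A reader might go further and infer that no HFA reference trend can exist. The documents do not support that. I.4 collects records retrospectively and XI.1 names a progression analysis, so earlier clinic fields may feed it. The 6 to 12 month interval is a background remark on typical practice, not a study schedule. What stands is that the source fields and period are unstated, and that using earlier fields would set trends from different periods against each other.

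A reader might also infer that six-month slopes are simply too noisy to show progression. That depends on an assumed SD and on what *biweekly* means: with twice-weekly testing, the chance of flagging a 2 dB/year loss reaches 40–67%. Single-subject detection is also not the same quantity as non-inferiority to HFA. On the paired scale, a low SD and a wide enough margin could make 50 subjects adequate, but the plan supplies neither figure. Nor do the documents give a progression rate, so a statement that almost no subject would progress cannot be made from them.

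**Conclusion.** The plan as written cannot deliver a conclusion of non-inferior progression detection. This rests only on what the documents contain: a non-inferiority hypothesis, a single agreement analysis, and no margin, bound rule or progression criterion. Six months of EyeSimplify data against HFA fields of unstated number and period add to the problem.

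The numerical part is illustrative. The individual slope SE is 1.9 to 2.9 dB/year with 13 two-weekly tests and 0.96 to 1.44 dB/year with 52 twice-weekly tests, given an SD of 1.0 to 1.5 dB and complete testing. The documents do not show that a six-month comparison is impossible in principle. They show that the inputs needed to judge it are missing.

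**What to change.** In I.5 and XI.1:
- Remove *non-inferior*. Restate the secondary hypothesis and Aim 2 as estimation of agreement between EyeSimplify MD and HFA MD: bias and 95% limits of agreement, each with a confidence interval.
- Use whatever routine HFA fields fall within a stated window of a home test. Enrolment happens at clinic appointments (VII.D.29) and testing starts within a week (VII.D.28), so some baseline pairs are likely, but none is guaranteed.
- Judge agreement against a dB limit fixed before the data are seen. The closure notice is dated 09/05/25; if the data have been seen, label the limit post hoc.
- Report EyeSimplify slopes descriptively with confidence intervals.
- State which HFA fields, and which period, feed any progression-analysis comparison.
- Draw no conclusion of non-inferior progression detection.

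The cost is wording and a more modest secondary claim. The paired analysis will also have fewer subjects if some lack an HFA field near a home test, which widens the limits as in step 6. Keeping the non-inferiority claim would instead need a common progression scale, a justified margin, a bound rule, defined HFA fields, longer follow-up and a matching sample size, and rewording cannot supply these.

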IV.3 *Are you requesting a [waiver of informed consent/authorization](#) (subjects will not be given any oral or written information about the study)?*
No

V. Other Committee Review

V.1 *Does this project involve any substance ingested, injected, or applied to the body?*

- *Do not answer yes, if the involvement includes a device, wire, or instrument*

No

V.2 *Are any contrast agents used for any purpose in this study?*

No

V.9 *Will any subject be asked to undergo a diagnostic radiation procedure (including radiographic, nuclear medicine, DEXA)?*

No

V.14 *Will any subject be asked to undergo a radiation therapy procedure (including external beam therapy, brachytherapy, or nuclear medicine therapy)?*

No

V.20 *Does this project involve the deliberate transfer of recombinant or synthetic nucleic acid molecules, or DNA or RNA derived from recombinant or synthetic nucleic acid molecules, into one or more human research participant?*

No

V.21 *Will any portion of this project be conducted in the CRU, or does it use any CRU resources?*

No

V.22 *Will this project use:*

- *any resource/patients of the Holden Comprehensive Cancer Center*
- *involve treatment, detection, supportive care, or prevention of cancer*

No

V.25.a *Will the study involve any of the following activity at UI Health Care, even if subjects or their insurance will not be billed for the item or service, and regardless of the study funding source (including studies with departmental or no funding)?*

- *Procedures, tests, examinations, hospitalizations, use of Pathology services, use of clinic facilities or clinical equipment, or any patient care services, including services conducted in the Clinical Research Unit; or*
- *Physician services or services provided by non-physicians who are credentialed to bill (ARNPs, Physician Assistants, etc.)*

Yes

V.25.b *Will there be any procedures or services that may happen as part of a subject's regular medical care and as part of the study?*

Yes

V.25.c *Will any study equipment or devices be supplied by a study sponsor?*

No

V.25.e *Is there or will there be an internal budget for this study?*

No

V.25.f *Is there or will there be an external budget for this study?*

No

V.26 *The study involves Department of Nursing Services and Patient Care nursing, nursing resources or evaluates nursing practices at UI Health Care.*
No

V.27 *Will the study involve the use of the I-CTMS (OnCore) for clinical trial data management? Select yes if any or all of the following apply:*

- *Any study required to register subjects in EPIC are encouraged to use the I-CTMS*
- *Best practice is to use the I-CTMS for any new study that involves subject tracking or sponsor invoicing*

Note: This question is for non-oncology studies only. For oncology studies use existing HCCC OnCore processes by selecting V.22
No

VI. Subjects

VI.1 *How many adult subjects do you expect to consent or enroll for this project?*
50

VI.2 *What is the age of the youngest adult subject?*
18.0

VI.3 *What is the age of the oldest adult subject?*
100.0

VI.4 *What is the percentage of adult male subjects?*
50

VI.5 *What is the percentage of adult female subjects?*
50

VI.6 *How many minor subjects do you expect to consent or enroll for this project?*
0

VI.13 *Describe EACH of your subject populations*

- *Include description of any control group(s)*
- *Specify the Inclusion/Exclusion criteria for EACH group*

Inclusion criteria: Patients older than 18 years of age with suspected, mild, moderate, or severe glaucoma

Exclusion criteria: Non-English speakers, patients with systemic or ocular disease affecting central vision, neurocognitive or psychiatric patients that are unable to perform testing, astigmatism >+2.00/-2.00 diopters

VI.14 *Provide an estimate of the total number of subjects that would be eligible for inclusion in each of your study populations (include your control population if applicable)*
450

VI.15 *Describe how you will have access to each of your study populations in sufficient number to meet your recruitment goals.*
Patients at the University of Iowa Hospitals and Clinics' Glaucoma clinic will be approached at the time of their scheduled appointments to determine if they are interested in participating in this research study.

VI.16 *Do you plan to recruit/enroll non-English speaking people?*
No

VI.18 *Do you propose to enroll any of the following in this study as subjects?*

- *Employee of the PI or employee of a research team member*
- *Individual supervised by PI or supervised by member of research team*
- *Individual subordinate to the PI or subordinate to any member of the research team*
- *Student or trainee under the direction of the PI or under the direction of a member of the research team*

No

VI.20 *Will subjects provide any information about their relatives?*
No

VI.23 *Will anyone (other than the subject) provide you with information about the subject (e.g. proxy interviews)?*
No

VI.26 *Is this project about pregnant women?*
No

VI.27 *Will this project involve fetuses?*
No

VI.28 *Does this project involve adult subjects who may be incompetent or have limited decision-making capacity on initial enrollment into the study?*
No

- VI.32 *Does this project involve subjects whose capacity to consent may change over the course of the study?*
No
- VI.37 *Does this project involve prisoners as subjects?*
No

VII.A. Project Description (A)

- VII.A.1 *Where will project procedures take place (check all that apply)?*
- UIHC - Glaucoma clinic
 - U.S. off-campus - Patients' homes via telemedicine
- VII.A.2 *Is this project also being conducted by other researchers at their own sites (e.g. a multi-site collaborative project)?*
No

VII.B. Project Description (B)

- VII.B.1. *Does this project involve any of the following (Check all that apply):*
- ☒ **Interventional** – Includes **Clinical (or Treatment) trial**, **Physiology intervention/study**, **Behavioral intervention/study**, **Diagnostic Trial**.
 - ☒ **Clinical (or Treatment) trial** – A prospective biomedical or behavioral research study of new treatments, new drug or combinations of drugs, new devices, or new approaches to surgery or radiation therapy. (NIH and [ClinicalTrials.gov](https://clinicaltrials.gov) & [FDA](https://www.fda.gov)) The University of Iowa requires a freestanding protocol.
 - ☐ **Physiology intervention/study** – A pharmacologic or measurement study aimed at understanding basic mechanisms of disease and/or of normal human physiology, often without any therapeutic intent (though a clinical trial could include such components, often labeled as “translational” or “basic science” aims.) Measurements in such studies could include, but are not limited to, a blood draw, EKG, EEG, MRI, auditory or sensory testing, checking vital signs, DEXA scans, eye tracking, specimen collection, exercise, fasting, special diets, etc.
 - ☐ **Behavioral intervention/study** – May be used to refer to studies of individual or group behavior. This option does not include drugs, biologics, or devices but could include psychotherapy, lifestyle counseling, behavior modification, etc.
 - ☐ **Diagnostic trial** – Protocol designed to evaluate one or more interventions aimed at identifying a disease or health condition ([ClinicalTrials.gov](https://clinicaltrials.gov) & [FDA](https://www.fda.gov))
 - ☐ **Observational**
 - ☐ **Expanded Access** – A process regulated by the Food and Drug Administration (FDA) that allows manufacturers to provide investigational new drugs to patients with serious diseases or conditions who cannot participate in a clinical trial. Examples of expanded access include non-protocol access to experimental treatments, including protocol exception, single-patient IND, treatment IND, compassionate use, emergency use, continued access to investigational drug, and parallel track ([ClinicalTrials.gov](https://clinicaltrials.gov) & [FDA](https://www.fda.gov)).
 - ☐ **Registry** – The collection and maintenance of data (not including biologic samples) in which: (1) the individuals in the registry have a common or related condition(s), and/or (2) the individuals in the registry are interested in being contacted for future studies by investigators other than those listed in Section II of this project. ([UI Guide](https://www.uiowa.edu))
 - ☒ **Repository** – The collection, storage, and distribution of human biologic samples and/or data materials for research purposes. Repository activities involve three components: (i) the collection of data and/or specimens such as blood, tissue, saliva, etc.; (ii) the storage of data or specimens, and data management function; and (iii) the sharing of data/specimens with recipient investigators other than the original investigators. (paraphrased from [OHRP](https://www.hhs.gov))
 - ☐ **Other**
- VII.B.1.a *Does this project involve any of the following (Check all that apply):*
- ☐ **Phase I trials** – include initial studies to determine the metabolism and pharmacologic actions of drugs in humans, the side effects associated with increasing doses, and to gain early evidence of effectiveness; may include healthy participants and/or patients ([ClinicalTrials.gov](https://clinicaltrials.gov) & [FDA](https://www.fda.gov))
 - ☐ **Phase II trials** – include controlled clinical studies conducted to evaluate the effectiveness of the drug for a particular indication or indications in patients with the disease or condition under study and to determine the common short-term side effects and risks ([ClinicalTrials.gov](https://clinicaltrials.gov) & [FDA](https://www.fda.gov))
 - ☐ **Phase III trials** – include expanded controlled and uncontrolled trials after preliminary evidence suggesting effectiveness of the drug has been obtained, and are intended to gather additional information to evaluate the overall benefit-risk relationship of the drug and provide an adequate basis for physician labeling ([ClinicalTrials.gov](https://clinicaltrials.gov) & [FDA](https://www.fda.gov))
 - ☐ **Phase IV trials** – studies of FDA-approved drugs to delineate additional information including the drug’s risks, benefits, and optimal use ([ClinicalTrials.gov](https://clinicaltrials.gov) & [FDA](https://www.fda.gov))
- VII.B.11 *Is there a separate, written protocol that will be submitted in addition to this IRB New Project form? (Note: a grant application is not considered to be a protocol)*

- VII.B.2** *Does this project involve a [drug washout](#) (asking subject to stop taking any drugs s/he is currently taking)?*
No
- VII.B.6** *Will any subjects receive a [placebo](#) in this study when, if they were not participating, they could be receiving an FDA-approved treatment for their condition?*
No
- VII.B.18** *Does this project involve the evaluation, or testing, of the safety and/or efficacy of a medical device?*
Yes
- VII.B.19** *Describe in detail procedures in place for maintaining device shipment and receipt records:*
EyeSimplify is a web browser-based visual field test and, therefore, will not require shipment or receipt records.
- VII.B.20** *Who will be responsible for maintaining these shipment and receipt records?*
EyeSimplify is a web browser-based visual field test and, therefore, will not require shipment or receipt records.
- VII.B.21** *Describe in detail procedures in place for tracking use and disposition of devices described in this study:*
The EyeSimplify web browser automatically tracks when subjects complete a visual field test and no additional physical record will be kept to minimize risk of loss of confidentiality.
- VII.B.22** *Who will be responsible for maintaining these use and disposition tracking records?*
The EyeSimplify web browser automatically tracks when subjects complete a visual field test and no additional physical record will be kept to minimize risk of loss of confidentiality. The PI and key research personnel will have access to the EyeSimplify web platform; however, M&S Technologies maintains this secure, encrypted, HIPAA-compliant database.
- VII.B.23** *Describe in detail procedures in place to limit access to authorized study personnel for the storage, control, and dispensing of the investigational devices. (For example, investigational devices are kept in a locked area away from approved devices or have a keyed interlock, and only study personnel authorized to dispense the device have the keys)*
EyeSimplify is a web-based visual field testing platform. Access requires subject-specific login credentials (created by a research assistant upon study recruitment) and to be granted tests (subjects will be unable to take an EyeSimplify visual field test if they do not have a test sent to them by a research team member, even if they have login credentials).
- VII.B.24** *Is the device FDA-approved for the way it will be used in this study?*
No
- VII.B.25** *Is there an IDE (Investigational Device Exemption) for this device in this research project?*
No
- VII.B.29** *Indicate the appropriate FDA status you and/or the sponsor are requesting for the use of this device in this study.*
Non-Significant Risk (NSR) device/software
- VII.B.31** *Provide a detailed rationale for why this device meets the FDA definition of a Non-Significant Risk Device (NSR)*
Per M&S, the EyeSimplify web browser-based visual field is "Class I" and doesn't need FDA Approval (highest-risk like neurostimulators) or FDA Clearance (medium-risk devices / 510(k)). They include it in their device listings on the FDA Establishment Registration (screen prints attached to additional documents section).
- Under 21 CFR 812.3(m), a "serious risk" device means an investigational device that:
1. Is intended as an implant and presents a potential for serious risk to the health, safety, or welfare of a subject;
 2. Is purported or represented to be for use supporting or sustaining human life and presents a potential for serious risk to the health, safety, or welfare of a subject;
 3. Is for a use of substantial importance in diagnosing, curing, mitigating, or treating disease, or otherwise preventing impairment of human health and presents a potential for serious risk to the health, safety, or welfare of a subject; or
 4. Otherwise presents a potential for serious risk to the health, safety, or welfare of a subject.
- The EyeSimplify web browser-based visual field test does not meet any of these criteria, qualifying it as a nonsignificant risk medical device.
- VII.B.32** *Provide a summary of prior investigations with this device.*
There are no prior research studies investigating the EyeSimplify visual field test.
- VII.B.33** *Have there been any prior IRB reviews (at UI or elsewhere) and/or determinations made with regard to this device?*
No
- VII.B.35** *Has the FDA made an assessment of risk with regard to this device?*
No
- VII.B.36** *Has this device/software been approved by the FDA for another indication or in another form from its use in this project?*
No

VII.C. Project Description (C)

- VII.C.1** *Does this project involve any [research on genes or genetic testing/research](#)?*
No

VII.D. Project Description (D)

- VII.D.1** *Check all materials/methods that will be used in recruiting subjects (you will need to attach copies of all materials at the end of the application):*
- Other - Patients at the University of Iowa Hospitals and Clinics' Glaucoma clinic will be approached at the time of their scheduled appointments to determine if they are interested in participating in this research study.

- VII.D.1.a** *Will any of the materials/methods below be used by researchers (or their colleagues) to recruit subjects into this study?*

- *the potential subject is a patient OR*
- *use of any information considered to be Protected Health Information (PHI) OR*
- *review of patient/clinic records be used in recruiting subjects*

Yes

- VII.D.1.b** *Describe source of records*

Patients at the University of Iowa Hospitals and Clinics' Glaucoma clinic will be approached at the time of their regularly scheduled appointments to participate in this research study.

- VII.D.1.c** *Select all Private Identifiable Information (PII) or Protected Health Information (PHI) accessed and used for this study (select all that apply)*

Identify types of PHI accessed

Type of PHI	Data source
Name	
Street address	
City	
County	
Precinct	
Zip code	
Geocodes smaller than state	
Date of birth, ages > 89 years of age	
Diagnosis dates	
Procedure dates	
Admission or discharge dates	
Telephone numbers	
Fax numbers	
E-mail addresses	
Social Security number	
Medical record number	
Health plan beneficiary or account numbers	
Certificate/license numbers	
Vehicle identifiers and serial numbers or license numbers	
Device identifiers or serial numbers	
Web URLs	
Internet Protocol (IP) address numbers	
Biometric identifiers including finger/voice prints	
Full face photographic images or any comparable images	
None of the above	

- VII.D.2.a** *List ALL of the variables, including any identifiers not previously entered or links to identifiers you plan to obtain/use for purposes of this study. (The information accessed should be the minimum data variables necessary for performing the desired analysis.)*

Data elements to be collected will include name, MRN, age, and glaucoma diagnosis/severity.

- VII.D.3** *Describe why you could not practicably recruit subjects without access to and use of the information described above*

Without the above, there would be many patients who would not meet inclusion or exclusion criteria after initial assessment. Using the above data will allow for a better patient experience while enrolling in this study, as well as better specificity in identifying the population we intend to recruit.

- VII.D.4** *Describe why you could not practicably obtain authorization from potential subjects to review their patient or clinic records for recruitment purposes.*

This study intends to review patients from a physician's practice panel to identify recruits. To request written authorization from all patients prior to identification for study inclusion or exclusion would require contacting all of the physician's patients prior to identification, for authorization to review records that the physician is already reviewing for their clinical care. This would require an inordinate amount of time, administrative labor and solicitation of thousands of patients.

- VII.D.5** *Describe plans to protect the identifiers from improper use or disclosure*

Only a "de-identified" aggregate data record will be kept in a central electronic database. The link between the subject, the medical record number, and the patient's project identifier will be maintained exclusively by the principal investigator and designated key research team members. The data record will be kept in an encrypted UIHC network drive specifically for protected research data, while the linking file will be kept in a similarly encrypted UIHC network drive in a separate file location. The files will also be password-protected.

Additionally, M&S maintains patient demographic and testing data in a secure, HIPAA-compliant, encrypted database. Patient names are encrypted when they are stored in the database. M&S only shares the information it collects with M&S-affiliated consultants and service providers, healthcare professionals using the product, and for law enforcement or judicial proceedings as permitted by law. Aggregate de-identified data may be used by M&S to improve their web-based testing software.

- VII.D.6** *Describe plans to destroy identifiers at the earliest opportunity consistent with conduct of the research*

Subjects will be identified in order to collect data for protocol-specific research, but the subjects' data will be de-identified immediately after the completion of data collection per HIPAA regulations. The identifiers will be electronically stored (as per the above-described encrypted, password-protected manner) and will be destroyed as soon as identifiers are no longer needed for protocol-specific research.

VII.D.7 *Does the research team agree that the requested information will not be reused or disclosed to any other person or entity, except as required by law, for authorized oversight of the study, or for other research for which the use or disclosure of the requested information would be permitted by the HIPAA Privacy Rule*
Yes

VII.D.8 *Will a member of the research team discuss the study with the subject in person prior to the subject agreeing to participate?*
Yes

VII.D.9 *Describe the physical location where the consent process will take place:*
The University of Iowa Hospitals and Clinics' Glaucoma clinic

VII.D.10 *Will a member of the research team discuss the study with the subject by phone prior to the subject agreeing to participate?*
No

VII.D.12 *Who will be involved in the [consent process](#) (including review of consent document, answering subjects' questions)?*

Name	Consent Process Involvement
